4.3 Blinding Procedure

Patients will be blinded to Group allocation. Anaesthetists, surgeons, and intensivists will have knowledge of Group identity. Similarly, it is expected that other surgical and nursing staff, and research staff conducting the in-hospital daily reviews, cannot be properly blinded to Group identity. But research staff conducting 1-12 mth follow-ups MUST be blinded to Group allocation.

4.4 Case Report Forms

For each form on which information is entered, the patient's initials, allocation number and the date of the visit must be entered in the appropriate space. The CRFs must be neatly handwritten with a black-ink ballpoint pen. Errors must be corrected by drawing a single line through the incorrect entry and writing in the new value positioned as close to the original as possible.

The correction must then be initialled and dated by the authorised individual making the change. Do not obliterate, write over, or erase the original entry when making a correction.

Case report forms should be opened as soon as possible following the start of screening and kept up to date as the patient continues the study.

As soon as possible after the end of each patient's participation in the study the CRF must be completed. All centres must store the paper based CRF according to GCP/ICP guidelines.

4.5 Web-based data entry

Following completion of the paper-based CRF, data will need to be entered by research staff to the database through a web-based data entry system. Further information can be found in the Procedures Manual. The system will audit the timeliness of data entry and reports will be generated the data monitoring committee regularly.

4.6 Data Base Production and Verification

Study data will be collected via the internet, monitored by the trial data management centre where all data fields are checked and automatically downloaded onto a database. At the end of the trial site-specific data will be sent to each site investigator on a CD, for long-term storage.

Study data will be collected in a paper based CRF, for transcription onto a web-database. We will maximize data quality and protocol standardization by arranging a start-up meeting at local scientific meetings or live streamed web based sessions, and will provide regular feedback to each centre via phone and the trial web-site, along with a monthly newsletter. A complete procedures manual will be produced. All study personnel will have 24-h access to the study coordinating centre to resolve any questions that arise. Further information can be found in the Procedures Manual.

4.7 Compliance Checks

Random audits of centres will be undertaken, to access the accuracy and legitimacy of the trial data. Statistical monitoring of the data completeness, data variance, and risk-appropriate endpoint rates will be done for all patient data.

4.8 Patient Completion/Withdrawal

All participants who are randomised will and undergo GA for surgery must be followed for the duration of the study (unless they withdraw consent) even if they are withdrawn from the active phase of the trial.

4.9 Repeat and Special Laboratory Tests

Serum electrolytes, haemoglobin/haematocrit, and a 12 lead ECG will be ordered preoperatively and if clinically indicated after surgery. All diabetics should have their HbA1C measured before surgery. Further tests will be ordered if clinically indicated.

4.10 Adverse Experiences

Serious adverse effects, serious adverse reactions, or suspected unexpected serious adverse reactions (SUSARs) are serious adverse events judged to be related to therapy.

At each visit/assessment, all adverse experiences either observed by the investigator or one of the clinical staff, or reported by the patient spontaneously or in response to a direct question will be evaluated by the investigator and noted in the adverse experience section of the patient's CRF. The nature of each experience, time of onset after surgery, duration, severity and relationship to treatment will be established. Any corrective treatment should be recorded on the appropriate pages of the CRF.

Adverse events should be documented at each assessment point throughout the study. Maximum intensity should be assigned to one of the following categories:

Mild - an adverse event which is easily tolerated by the patient, causing minimal discomfort and not interfering with everyday activities.

Moderate - an adverse event which is sufficiently discomforting to interfere with normal everyday activities.

Severe - an adverse event which is incapacitating and prevents normal everyday activities and/or requires therapeutic intervention (i.e. use of a prescription drug or hospitalisation).

Any serious adverse event should be reported by the local site investigator or research assistant within 24 hours by telephone or email to the local site investigator. Note that study endpoints do not need to be included as serious adverse events.

A preliminary telephone report should be followed by a full report which includes copies of relevant hospital case records, autopsy reports and other documents, where applicable.

A serious adverse experience is defined as any event which is fatal, life-threatening, permanently disabling or incapacitating or results in hospitalisation, prolongs a hospital stay or is associated with congenital abnormality, carcinoma or overdose.

Life threatening means that the patient was at immediate risk of death from the event as it occurred, ie. it does not include a reaction that, had it occurred in a more serous form, might have caused death. For example, drug induced hepatitis that resolved without evidence of hepatic failure would not be considered life threatening, even though drug induced hepatitis can be fatal.

Permanent disability means a permanent and substantial disruption of a patient's ability to carry out normal life functions.

More details for Adverse Event reporting will be found in the procedures manual.

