2. BACKGROUND

Anaesthetists typically manage perioperative hypotension in the first instance with an intravenous (IV) fluid bolus of a balanced salt crystalloid solution, or sometimes with one of several colloids. If persistent or more profound hypotension occurs, particularly in the intraoperative period when anaesthetic drug-induced vasodilation is common, an IV vasoconstrictor (typically metaraminol bolus prn) is used. Similar approaches are used in the intensive care unit (ICU) and surgical wards. We simply don't know whether using a 'liberal' fluid strategy based primarily on supplemental IV fluids, or a 'restrictive' strategy based on altered haemodynamic goals and/or vasopressor drug therapy, is best for most patients undergoing major surgery. The evidence base for fluid management in the postoperative setting is poor and is insufficient to guide our practice (1-4). Anaesthetists, intensivists and surgeons differ in their approaches to perioperative fluid therapy (5, 6).

Around 250 million people undergo major surgery each year around the world (7), with about 2 million being in Australia (1 in 10 Australians), and a growing proportion (now 40%) being elderly. By 2056 in Australia, more than 8.5 million anaesthetics (>50%) will be administered to patients over the age of 65 (8). These patients and many others have co-existent medical diseases that add risk to the procedure. The personal, social and economic consequences of postoperative complications, additional hospital stay, and long-term disability, are great.

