3.3.2 Perioperative Management

Preoperative period

ERAS perioperative care principles will be emphasized. All patients will receive prophylactic antibiotics according to established guidelines. Medications will be continued perioperatively unless or at the clinicians discretion, but we will recommend withholding ACE-inhibitors and ARBs on the day of surgery. We will record preoperative use of bowel preparation, fasting times, ERAS data, medications, and biochemistry and haematology results on the CRF.

Intraoperative period

Choice of anaesthetic agents and perioperative analgesia will be left to the discretion of the anaesthetist; such data will be recorded. We will emphasize the need to avoid hypothermia (<36 °C). Epidural use will be recorded as this may

increase the risk of hypotension and need for IV fluids (64, 65), but such effects are likely to be small (66). We will record usage of all "advanced" monitoring devices (CVP, pulse contour analysis, TOE, oesophageal Doppler).

The acceptable limits of low BP, and a definition of 'hypotension', vary widely (67), though such a definition will be modified by older age, pre-existing hypertension, and cerebrovascular disease. We will use a general guideline of systolic BP <90 mmHg for more than 5 mins, but also ask the attending anaesthetist to modify their acceptable lower limit of sBP at the commencement of surgery, and, according to randomly-assigned group, treat hypotension with additional IV fluid or vasopressor therapy (see below). For example, in younger patients or those with pre-existing low BP it may be acceptable to tolerate a sBP of 85-95 mmHg, but in older patients, particularly those with pre-existing hypertension, a higher lower limit may be required. Such modification to the acceptable lower sBP will be recorded. For patients managed in a high dependency or ICU environment after surgery, hypotension will be similarly treated for the first 24 h after surgery.

Postoperative period

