The Restrictive protocol group is designed to provide less than 2.0 L water and 120 mmol sodium per day. Induction of anaesthesia will be accompanied by an IV fluid bolus limited to ≤5 ml/kg; no other IV fluids will be used at the commencement of surgery (unless indicated by goal-directed device [see below]). Hartmann's balanced salt crystalloid 5 ml/kg/h will be administered until the end of surgery, and bolus colloid/blood used intraoperatively to replace blood loss (ml for ml); then an infusion at 0.8 ml/kg/h until expedited cessation of IV fluid therapy within 24 hours. The rate of postoperative fluid replacement can be reduced if there is evidence of fluid overload and no hypotension, and can

be increased if there is hypotension AND evidence of hypovolaemia. For a 75-kg patient and 4 h operation, intraoperative fluid volume will be 1875 ml (+colloid/blood replacement for blood loss). The first 24-h fluid administration will be around half that of the liberal group (P.T.O).

Hypotension will be initially treated with fluid boluses in the liberal protocol group, and with a vasoconstrictor in the restrictive protocol group. The latter will consist of metaraminol or phenylephrine bolus/infusion and/or noradrenaline infusion during surgery, and a noradrenaline infusion postoperatively if in a HDU or ICU environment. The lower limit of acceptable sBP in the restrictive group can be further reduced by the attending anaesthetist or intensivist in order to limit fluid replacement or potentially unnecessary inotropic support (as per above). We have laminated instructional flowcharts for the anaesthetists and postoperative (ward or ICU/HDU) medical and nursing staff caring for the study patients (see Appendix). Research staff will be present at or soon after all handover steps, and be contactable at all hours.

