4.2 Goal-directed Therapy

For anaesthetists employing advanced monitoring (eg. CVP or goal-directed device), we allow additional colloid fluid supplementation to augment a haemodynamic target. It is likely to lead to additional colloid administration during and after surgery (3, 4, 45). Some hospitals use pulse contour analysis to direct perioperative or ICU fluid therapy in surgical patients, and some use oesophageal Doppler. Most rely upon conventional monitoring (HR, BP, urine output). We plan to test the effectiveness of each approach according to their local availability and use. The statistical analysis will focus

on a test for interaction, to determine whether the effects of a fluid regimen work differently in those with and without any advanced monitoring. We anticipate that more than half will use (only) clinical measures.

For each of the goal-directed techniques, pulse/stroke volume variation or FTc will be measured before commencement of surgery and repeated at regular (say, 10-30 min) intervals intraoperatively. For those in the liberal protocol group, goal-directed therapy can continue postoperatively at 4 hourly intervals, for up to 24 hours after surgery. If there is evidence of fluid responsiveness (eg. systolic pressure/volume variation of ≥13% (77)) at any of these times then IV colloid or crystalloid 3-5 ml/kg can be given. Such data will be collected on the CRF.

Colloid* (recommended) or crystalloid (3 ml/kg)	Liberal	Restrictive
Colloid/blood (using a transfusion threshold) bolus if acute bleeding	Yes	Yes
If normotensive but monitoring suggests hypovolaemia (eg. CVP<5 or oliguria)	Yes	No
If normotensive but goal-directed device suggests hypovolaemia (eg. FTc <0.33, ΔSV ≥10%, or SVV≥13%)	Yes	Consider
If hypotensive (1) and hypovolaemia	Colloid*	Colloid* (but limit) + vasoconstrictor
(2) but not hypovolaemic	Colloid* ± vasoactive	vasoactive therapy

^{*} starch-based colloids are not recommended (30, 34)

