- 11. Total hospital stay, including any readmission up to day 30.
- 12. Quality of recovery: QoR-15 score on days 1, 3 and 30.
- 13. The rates of serious adverse events, and severity of adverse events (mild, moderate, severe), classified by organ system.

STATISTICAL ANALYSES

Primary endpoint: disability-free survival

Disability free survival will be displayed with Kaplan-Meier plots, and described with event-free proportions in each treatment arm obtained from these plots at days 1, 30, 90, 180 and 365 days post-surgery. Comparison of overall time to events between treatment arms will be made using the log rank test and the Cox proportional hazards model to provide a hazard ratio and 95% CI. Assessment of proportionality of hazards will be based on tests using Schoenfeld residuals. The principal analysis will not impute missing WHODAS measurements for patients known to be alive at those assessment times. The first sensitivity analysis will impute all missing WHODAS assessments for subjects known to be alive at those assessment times by giving them a disabled score (WHODAS of 24). A second sensitivity analysis will impute the missing WHODAS assessments using multiple imputation, with the imputation model employing baseline and post-baseline information predictive of missingness or WHODAS scores, separately in each treatment arm, with results combined across imputations using Rubin's rules.

Alternative 'new onset' definition of the primary endpoint

Analysis of disability-free survival based on the `new onset' persistent disability definition will follow the same approach as for the primary endpoint.

Time to death

Analysis of time to death will follow the same approach as for the primary endpoint.

Other outcomes

Secondary outcomes measured on a binary scale (1, 2, 3, 4, 8, 9) will be summarised using proportions in each treatment arm and analysed using binomial regression with a logarithmic link to estimate Risk Ratios with 95% CIs and p-values, or exact logistic regression to approximate Risk ratios if the number of events in either arm is fewer than 10. Should there be convergence difficulties with log-binomial regression, a log-Poisson model will be employed with robust standard errors.

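### The severity scale grades any event needing a prescription drug as Severe, and allocation decides whether hypotension is first treated with a drug or with fluid, so the adverse-event severity table could be biased against the restrictive arm

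*Protocol*

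**What the plan says.** **Severity scale (Protocol 4.10).** Severe is an adverse event "which is incapacitating and prevents normal everyday activities and/or requires therapeutic intervention (i.e. use of a prescription drug or hospitalisation". Moderate is "an adverse event which is sufficiently discomforting to interfere with normal everyday activities". Mild, like Moderate, is defined by discomfort and function, with no reference to treatment.

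**Treatment of hypotension (Protocol 3.3.2 and 4.1).** Anaesthetists are asked to "according to randomly-assigned group, treat hypotension with additional IV fluid or vasopressor therapy". Section 4.1 is specific: "Hypotension will be initially treated with fluid boluses in the liberal protocol group, and with a vasoconstrictor in the restrictive protocol group". The vasoconstrictor is "metaraminol or phenylephrine bolus/infusion and/or noradrenaline infusion during surgery", and noradrenaline after surgery for patients in HDU or ICU. Section 4.1 also lets the acceptable lower limit of systolic pressure be reduced further in the restrictive group.

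**Reporting (SAP, secondary endpoint 13).** "The rates of serious adverse events, and severity of adverse events (mild, moderate, severe), classified by organ system".

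**Timing and blinding.** The flow chart in Protocol 3.3.1 records adverse events on the day of surgery, day 1, day 3 and day 30. Staff doing in-hospital daily reviews are not expected to be blinded (4.3 and 5). Section 5 requires blinding of research staff for the day 3 and 1 to 12 month follow-ups; section 4.3 requires it for 1 to 12 months only.

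**The concern.** A severity grade should describe the event. Here one route to the top grade is the treatment given, and for hypotension the first treatment is what the trial randomises. A patient whose pressure falls and who receives metaraminol meets the drug clause. A patient with the same fall who receives a fluid bolus need not, and may be graded Mild or Moderate.

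At stake is how the safety results read. An excess of Severe cardiovascular events under fluid restriction would look like harm, yet could arise with identical haemodynamics in both arms. The first two scheduled assessments, on the day of surgery and day 1, fall when the randomised strategy is in force and the in-hospital reviewers know the allocation.

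**Working it through.** The documents give no rate of hypotension, vasopressor use or adverse events, so there is no stated figure to reproduce. The check has two parts.

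**1. Does the wording produce the effect?**

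- 4.10: drug treatment is sufficient for Severe because the two limbs are joined by and/or. Mild and Moderate have no such limb.
- 3.3.2 and 4.1: allocation determines whether the first treatment is a drug or fluid.
- 4.10 covers all adverse experiences that are observed or reported. Nothing there excludes hypotension or exempts treatment directed by the protocol.
- The scale does not say whether IV fluid is a prescription drug. The Background sets supplemental fluid against a "strategy based on altered haemodynamic goals and/or vasopressor drug therapy", which suggests it is not, but that passage is not a grading rule.

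Under the rule as written, then, identical episodes can receive different grades by arm, provided that hypotension is recorded and fluid does not count as a drug.

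**2. How large could it be?** All rates below are assumptions. Let

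- h = share of patients with hypotension recorded as an adverse event, equal in both arms;
- v = share of those given a vasoactive drug (v_R restrictive, v_L liberal);
- b = share with a Severe event for other reasons, equal in both arms and independent.

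Then P(any Severe event) = 1 − (1 − b)(1 − h·v).

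Worked case: h = 20%, b = 20%, v_R = 90%, v_L = 30%.

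- Restrictive: 1 − 0.80 × (1 − 0.18) = 1 − 0.656 = 34.4%
- Liberal: 1 − 0.80 × (1 − 0.06) = 1 − 0.752 = 24.8%
- Ratio: 34.4 / 24.8 = 1.39, with no true difference.

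Risk ratios for any Severe event with b = 20%:

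| h | v 70% vs 50% | v 90% vs 30% | v 100% vs 0% |
|---|---|---|---|
| 2% | 1.02 | 1.05 | 1.08 |
| 5% | 1.04 | 1.11 | 1.20 |
| 10% | 1.07 | 1.21 | 1.40 |
| 20% | 1.11 | 1.39 | 1.80 |

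The ratio depends on b. With b = 10%, the h = 2% row becomes 1.03 to 1.18 and the h = 20% row 1.19 to 2.80. The last column is a limiting case, because the bolus table in 4.2 permits vasoactive drugs in the liberal arm.

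Among hypotension events alone, the ratio of Severe grades from the drug clause is v_R / v_L: 0.7 / 0.5 = 1.4, or 0.9 / 0.3 = 3.0. A cardiovascular row would be diluted by whatever other events it contains.

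If grading ignores the treatment given (modelled as v_R = v_L), the ratio is 1.00 for every h and b.

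**The case against.** The case against has several parts, and most of it limits the point rather than removing it.

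- **The two conditions are open.** A fluid or colloid bolus is plainly an intervention. If prescribed fluid counts as a prescription drug, the gap narrows or closes. Hypotension is handled in the protocol as a managed haemodynamic state and is nowhere listed as an adverse event. Further reporting rules are in the Procedures Manual, which is not among the documents. This stands: the table could be biased, and the documents do not show that it is.
- **The treatment contrast is partial.** For a hypotensive patient who is not hypovolaemic, the 4.2 table gives the liberal arm "Colloid* ± vasoactive". With hypovolaemia, the restrictive arm receives limited colloid as well as a vasoconstrictor. After surgery, 4.1 names a vasoconstrictor only for HDU or ICU. The lower pressure limit allowed in the restrictive arm may also reduce the episodes counted there. This stands, although that limit is a second influence that depends on allocation and does not correct the first.
- **Blinding.** A reader might infer that all severity grading is done by staff who know the allocation. The documents do not support that: section 5 requires blinding from day 3 on. The unblinded grading mainly concerns the day of surgery and day 1.
- **The endpoint is minor.** Severity is item 13 of 13 in the SAP, is absent from the secondary endpoints in Protocol 3.3.3.2, and has no analysis method: the SAP's method lists name only items 1 to 12. That the table is split by arm is an inference, though a natural one. This stands, but a descriptive table can still mislead.

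A reader might also infer that the scale fails for inpatients generally, since many treated events receive a prescribed drug. That limits discrimination in both arms alike and does not create a difference between them, so it is not part of this point.

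**Conclusion.** The concern holds in conditional form. As worded, the scale and the allocated treatment of hypotension allow the same episode to be graded Severe in the restrictive arm and lower in the liberal arm. The direction is against the restrictive arm, mainly for cardiovascular events.

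This rests on two assumptions: that hypotension is recorded as an adverse event, and that IV fluid is not counted as a prescription drug. The size cannot be derived from the documents. On the assumed rates tabulated above it runs from negligible (1.02) to large (1.80), and it changes with the assumed background rate of Severe events.

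A reader might infer that the trial's main safety or efficacy conclusions are compromised. They are not. The primary endpoint does not use this scale, and 4.10 defines seriousness separately, without a drug-treatment criterion, so serious-adverse-event rates are untouched.

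**What to change.** **In SAP item 13:** report hypotension events separately by arm, without a severity grade, and leave them out of the mild/moderate/severe table. Add a note that the arm-specific lower pressure limit allowed in Protocol 4.1 may also affect these counts. This is one or two sentences and works with data already collected.

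**For any grading still to be done:** remove the treatment limb from Severe in Protocol 4.10 and grade by effect on the patient. Use the same definition in both arms. Do not grade against the modifiable pressure limit, because it can be lowered further in the restrictive group and would make the grade depend on allocation again.

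**Cost:** hypotension loses its severity grade, and events already graded stay on the old scale. The change to 4.10 can reach few patients: 2,578 of the planned 3,000 (86%) were already enrolled at the sample-size review discussed in June 2016, and the SAP is dated August 2017. The SAP sentence is therefore the part that matters. Neither change affects clinical management.
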